8.4.6 Ophthalmic Assessments

In this study, ophthalmic assessment including confirming the history, and risk factor of cataract will be performed to confirm the existence of cataract at assessment time points. If the presence of a cataract is suspected, detailed examinations (ex. slit lamp examination etc.) should be performed (see [Table 8-1](#)). Because the risk of cataract increases with use of treatment such as steroids. SAA patients might be pre-medicated with steroids for ATG, therefore having this assessment at baseline would be helpful to assess causality to study treatment.

8.4.7 Other safety evaluations

These tests are being performed to screen for occult infections so that appropriate medical management per institutional practice can be started prior to initiation of study treatment.

Chest X-ray

Standard chest X-ray (PA view) will be performed at screening except for those who have had a CT scan of the chest done within 1 month of Day 1.

Abdominal sonography

Standard abdominal ultrasound scan including liver, gallbladder, spleen, pancreas and kidney will be performed at screening.

Clinically significant abnormalities present when the participant signed the informed consent should be reported as Medical History on the appropriate eCRF. New or worsened clinically significant findings occurring after informed consent must be recorded as an AEs on the eCRF.

8.4.8 Appropriateness of safety measurements

The safety assessments selected are standard for this participant population.

Cytogenetic abnormalities, clonal evolution to PNH, evolution to MDS or AML will be evaluated in this study. A serious complication of aplastic anemia is its evolution to clonal hematologic diseases such as MDS and leukemia, which is usually associated with the appearance of a cytogenetic abnormality in bone marrow cells. The actuarial risk for this complication has been estimated in other studies at around 15% at 5 years. Conversion from normal to abnormal karyotype occurred at a constant rate after initial diagnosis, with about 50% of cases developing within the first 30 months ([Maciejewski et al 2002](#)). In CETB115AUS01T, clonal evolution occurred in 9 of 123 (7%) participants, which is within the range that would be expected with immunosuppression alone at 2 years after the initiation of treatment ([Townsley et al 2017](#)), while the estimated probability of being clonal evolution-free was above 90% up to 2 years. These data have since been updated by Novartis, and at the update cutoff of (28-Feb-2018), clonal evolution occurred in 15/154 (10%; vs. 7% at the original cutoff) which is consistent with the reported incidences of clonal evolution in SAA participant receiving first line treatment with IST alone (without the addition of eltrombopag). In the refractory AA patients treated with eltrombopag, evolution to an abnormal karyotype occurred in 16 (19%), and it is almost always an early event occurring within 6 months after initiation of eltrombopag ([Winkler et al 2019](#)).

8.5 Additional assessments

8.5.1 Pharmacokinetics

8.5.1.1 Pharmacokinetic blood collection and handling

Blood samples (2 mL/sample) for eltrombopag PK evaluation will be collected from all participants who receive at least one dose of eltrombopag.

It is noted that participants must have received once daily eltrombopag for at least 7 consecutive days prior to the planned PK sampling day to ensure the PK sample drawn at steady state (i.e., no dose interruptions or missing for at least 7 consecutive days). If a participant discontinued eltrombopag treatment or eltrombopag has been reinitiated after a dose interruption within the 7 days prior to the planned PK sampling day, the planned PK sampling should not be collected, instead PK sampling should be performed after continuing eltrombopag treatment at least for 7 days (actual date and time will be recorded).

The scheduled PK sample collection will be only conducted in core treatment period. PK blood sampling will be performed as indicated in the Visit Evaluation Schedule ([Table 8-1](#)). The details of scheduled sampling time points for eltrombopag PK are shown in [Table 8-4](#). Considering the clinical feasibility of blood collection, the patients will be required to take the dose at morning.

Intensive PK sample collection :

Twelve Chinese adult participants and all Japanese pediatric participants will receive intensive PK sampling over a 24 hours period on Days 14 to 15 after the initial dose of eltrombopag, in order to provide evaluable full PK profiles. A total of 6 blood samples will be collected at the following time points: pre-dose (trough), and 2, 4, 6, 8, and 24 hours post-dose. When these participants reduce to the lower dose levels, one trough blood sampling each will be collected at pre-dose on the 15th day after each new dose has started.

Sparse PK sample collection :

For all remaining participants, one trough blood sample each will be collected at pre-dose on the 15th day after the initialization of eltrombopag treatment and at pre-dose on the 15th day after each new dose has started until the lowest dose is reached.

Table 8-4 Pharmacokinetic blood collection log (eltrombopag)

Week from the first dose	Day from new dose started	Scheduled time point	Dose reference ID	Sample number
2	14	0 h (Pre-dose) ^a	1 ^b /101 ^c	1*
2	14	2 h (± 15 min)	1	2*
2	14	4 h (± 30 min)	1	3*
2	14	6 h (± 30min)	1	4*
2	14	8 h (± 30min)	1	5*
2	15	24 h (± 1 h)/0 h (Pre-dose) ^a	1 ^c /102 ^b	6
Variable	15	24 h (± 1 h) ^d /0 h (Pre-dose) ^{a,d}	2+ ^e /103+ ^f	7+ ^g
Unscheduled	Unscheduled	Unscheduled ^h	NA	1001+ ^h

Week from the first dose	Day from new dose started	Scheduled time point	Dose reference ID	Sample number
* ^a : these samples are only collected for 1) the first 12 Chinese adult participants who signed the informed consent to participate in the PK study, receiving 75 mg/day, 2) all Japanese pediatric participants at initial dose. a: Collect PK sample immediately before drug administration (not more than 1 h prior to dosing); b: Dose administration record after PK sampling ; c: Dose administration record before PK sampling; d: Collect pre-dose PK blood sample on the 15 th day after each new dose has started (dose reduction criteria: 75, 50 and 25 mg/day for the participants \geq 12 years old; 37.5, 25 and 12.5 mg/day for participants \geq 6 and < 12 years old); e: Dose reference ID will be sequentially numbered 2, 3 for the last dose prior to pre-dose PK sampling after each new dose started, f: Dose reference ID will be sequentially numbered 103,104 for dose after pre-dose PK sampling; g: Sample number will be sequentially numbered 7, 8 when the PK blood sample is taken at pre-dose on Day 15 after each new dose started; h: Unscheduled PK blood samples may be collected at any time for measurement of plasma drug concentrations if clinically indicated or at the Investigator's discretion and will be uniquely, sequentially numbered as 1001, 1002, etc.				

In case of DILI, an unscheduled eltrombopag PK sample should be collected.

On the days of PK sample collection, the participant will be advised to take investigational drug after the pre-dose blood sample is taken.

The sample collection must be captured on appropriate eCRF and requisition form(s). The actual date and time of each PK sample collection will be integrated in the eCRF via data transfer.

Additionally, for PK analysis purposes, the following information about the most recent dose prior to the visit (or DILI) will be recorded in the eCRF:

- Date and time of dosing.
- Whether or not eltrombopag was taken at empty stomach (1 hour before or 2 hours after a meal) or at least 2 hours before or 4 hours after polyvalent cations and dairy products.
- Whether or not the participant vomited after receiving eltrombopag within 4 hours of dosing.

8.5.1.2 Analytical method

The plasma samples will be assayed for eltrombopag concentrations using a validated liquid chromatography – tandem mass spectrometry assay (LC-MS/MS). The lower limit of quantitation (LLOQ) will be 100 ng/mL.

Concentration values below the LLOQ will be reported as zero, and missing samples will be labeled accordingly. Further refinements of these bioanalytical methods may be conducted during the course of the study.

Plasma samples remaining after completion of the determination eltrombopag concentrations may be used for exploratory assessments (e.g., metabolite identification), as appropriate. All relevant information will be provided in the [Laboratory Manual].

9 Study discontinuation and completion

9.1 Discontinuation

9.1.1 Discontinuation of study treatment

Discontinuation of study treatment for a participant occurs when study treatment is permanently stopped earlier than the protocol planned duration and can be initiated by either the participant or the investigator.

The investigator must discontinue study treatment for a given participant if, he/she believes that continuation would negatively impact the participant's well-being.

Study treatment must be discontinued under the following circumstances:

- The hematologic response is assessed as NR at Week 26.
- Diagnosis of relapse.
- Participant/guardian decision.
- Pregnancy.
- Any of the following is observed: a new clinical significant morphological, chromosomal or cytogenetic abnormality*, diagnosis of myelofibrosis^{**} or progression to MDS or AML.
- Participant meets any of the stopping criteria in [Section 6.5.1](#).
- Any laboratory abnormalities that in the judgment of the investigator, taking into consideration the participant's overall status, prevents the participant from continuing the study treatment.
- Use of prohibited treatment as per recommendations in the prohibited treatment section (see [Section 6.2.2](#)).
- The participant is withdrawn from the treatment with planned r-ATG or CsA, or the participant cannot tolerate the planned study treatment (e.g. Infusion-related r-ATG reactions refractory to all appropriate supportive measures; Life threatening acute hypersensitivity reactions).
- The participant has an unacceptable AE whose causal relationship with eltrombopag cannot be ruled out.
- The participant is found to be significantly non-compliant with the requirements of the protocol (including treatment non-compliance).
- The investigator (or sub-investigator) believes that the participant will not benefit from eltrombopag or
- that the participant needs to transfer to other therapy (e.g. HSCT, ATG/ALG).
- The study is prematurely terminated.
- Any situation in which study participation might result in a safety risk to the participant.

*: Discontinuation should be considered if any new chromosomal or cytogenetic abnormality is observed, and if considered significant should be discontinued. This also applies for participants that started treatment based on normal karyotyping while FISH results were not yet available.

**: Considering TPO-receptor agonists like eltrombopag might lead to pathological increase in reticulin or collagen fibers by chronic stimulation of megakaryocytes. It is highly recommended to consider discontinuation of eltrombopag if a pathological myelofibrosis (e.g. staining for fibrosis is Grade 3 or higher) is confirmed.

Participants may voluntarily discontinue from the study treatment (eltrombopag and/or r-ATG and/or CsA) for any reason at any time. If discontinuation of study treatment occurs, the investigator should make a reasonable effort to understand the primary reason for the participant's premature discontinuation of study treatment and record this information.

Participants who discontinue study treatment or who decide they do not wish to participate in the study further should NOT be considered withdrawn from the study UNLESS they withdraw their consent (see [Section 9.1.2](#)). **Where possible, they should return for the assessments indicated** in the Assessment Schedule. If they fail to return for these assessments for unknown reasons, every effort (e.g. telephone, e-mail, letter) should be made to contact the participant/pre-designated contact as specified in the lost to follow-up section (see [Section 9.1.3](#)). This contact should preferably be done according to the study visit schedule.

If the participant cannot or is unwilling to attend any visit(s), the site staff should maintain regular telephone contact with the participant, or with a person pre-designated by the participant. This telephone contact should preferably be done according to the study visit schedule.

After study treatment discontinuation, at a minimum, in abbreviated visits, the following data should be collected at clinic visits or via telephone/email contact:

- New / concomitant treatments
- AEs / SAEs
- Clonal evolution assessments

The investigator must also contact the IRT to register the participant's discontinuation from study treatment.

Participants who prematurely discontinue study treatments will have efficacy assessments at defined time points (Week 13, Week 26, Week 52 and yearly after), unless or until the occurrence of no response at Week 26, relapse or alternative SAA treatment (whichever comes first). Survival and clonal evolution data will be collected for all participants up to Year 3 (Week 156).

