6.1 Study treatment

The investigational drug for this study is eltrombopag (ETB115). The study treatment includes eltrombopag, r-ATG and CsA.

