6.5.1.2 Dose reduction/interruption due to liver function abnormalities and thrombosis/embolism

Eltrombopag dose may be interrupted when clinically indicated at the discretion of the investigator. Serum ALT, AST and bilirubin (total, direct and indirect) should be measured prior to initiation of eltrombopag, every 2 weeks while adjusting the dose and monthly after establishment of a stable dose. Abnormal serum liver function tests (LFTs) should be evaluated with repeat testing preferably within 48-72 hours (see [Table 6-7](#) and [Section 6.5.2.1](#)). If the abnormalities are confirmed, serum liver tests should be monitored weekly until the abnormalities resolve, stabilize, or return to baseline levels. Alternative causes of LFT elevations, such as hepatitis or concomitant medications (e.g., cyclosporine A) must always be investigated.

NOTE: Eltrombopag is known to cause interference in measurement of total bilirubin, which may lead to falsely increased levels of total bilirubin (see [Section 8.4.1](#)). Please take dose modification decision based on direct (conjugated) bilirubin (DBIL) along with ALT and/or AST (see [Table 6-7](#) below).

[Table 6-7](#) summarizes the recommendations for dose interruption or reduction of eltrombopag in the management of liver function abnormalities and thrombosis/embolism events. For participants who fulfill the criteria of eltrombopag discontinuation in [Table 6-7](#), refer to [Section 9.1](#) for the further action to be taken after discontinuation.

Table 6-7 Guidelines for eltrombopag dose modification based on liver function abnormalities and thrombosis/embolism

Criteria	Action
Isolated AST or ALT elevation	
> ULN - 3 x ULN	Maintain dose level.
> 3 - 5 x ULN	Maintain dose level. Repeat liver function test (LFTs) ^a as soon as possible, preferably within 48-72 hours from awareness of the abnormal results. If abnormal lab values are confirmed upon the repeat test, then monitor LFTs ^a weekly, or more frequently if clinically indicated, until resolved to \leq 3.0 x ULN. Discontinue participant from eltrombopag if elevation is combined with any of the following: 
 • Clinical symptoms of liver injury or evidence for hepatic decompensation • Persistence for \geq 4 weeks
> 5 - 10 x ULN	Interrupt dose.

Criteria	Action

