	
Repeat LFTs^a as soon as possible, preferably within 48-72 hours from awareness of the abnormal results. If abnormal lab values are confirmed upon the repeat test, monitor LFTs^a weekly, or more frequently if clinically indicated, until resolved to $\leq 3.0 \times$ ULN, then:
 
If resolved in ≤ 14 days, then resume at same dose level; If toxicity recurs at same dose, then follow the above guideline and resume dose at a lower dose level (decrease by one level^c)
 
If resolved > 14 days and ≤ 28 days, then decrease one dose level^c
 
If not resolved within 28 days, then discontinue participant from study treatment

$> 10 - 20 \times$ ULN	
Interrupt dose.
 
Repeat LFTs^a as soon as possible, preferably within 48-72 hours from awareness of the abnormal results. Monitor LFTs^a weekly, or more frequently if clinically indicated, until resolved to $\leq 3.0 \times$ ULN. If resolved within 28 days, decrease by one dose level.
 
If not resolved to $\leq 3.0 \times$ ULN within 28 days, then discontinue participant from study treatment.

$> 20 \times$ ULN	
Discontinue participant from study treatment.
 
Repeat LFTs^a as soon as possible, preferably within 48-72 hours from awareness of the abnormal results. If abnormal lab values are confirmed upon the repeat test, monitor LFTs^a weekly, or more frequently if clinically indicated until resolved to baseline or stabilization over 4 weeks.

Combined^b elevations of AST or ALT and direct bilirubin (DBIL)	

For participants with normal baseline ALT and AST and DBIL value, [AST or ALT $> 3 \times$ ULN] combined with [DBIL $> 2 \times$ ULN] without evidence of cholestasis
 
OR
 
For participants with elevated baseline ALT or AST or DBIL, [AST or ALT $> 3 \times$ baseline] OR [AST or ALT $> 5 \times$ ULN], whichever is lower, combined with [DBIL $> 2 \times$ baseline AND $> 2 \times$ ULN]
	
Discontinue participant from study treatment
 
Repeat LFTs^a as soon as possible, preferably within 48 hours from awareness of the abnormal results, then weekly or more frequently (if clinically indicated) monitor LFTs^a, or more frequently if clinically indicated, until ALT, AST or DBIL have resolved to baseline or stabilization over 4 weeks.
 
Evaluate the possibility of DILI (Section 6.5.2.1)

Thrombosis/embolism	

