Deep vein thrombosis, pulmonary embolus, transient ischemic attack (TIA) or stroke, myocardial infarction at any time while on eltrombopag	
Discontinue participant from eltrombopag.
 
If the platelet level is $> 50 \times 10^9/L$ at the time of thrombosis, treatment with enoxaparin or another appropriate anticoagulant is recommended as clinically indicated until the platelet count drops $< 20 \times 10^9/L$ or a standard 3 to 6 month course of anticoagulation is completed.

^a Core LFTs consists of ALT, AST, GGT (Gamma-glutamyl transferase), total bilirubin (direct and indirect), and alkaline phosphatase (ALP)
 
^b "Combined" is defined DBIL increase to the defined threshold concurrently with ALT/AST increase to the defined threshold. If the bilirubin increase is below the defined threshold, guidance for isolated AST or ALT elevation should be followed
 
^c Dose level: for participants ≥ 12 years old, one dose level is 25mg; for participants < 12 years old, one dose level is 12.5mg.
	

Definition of discontinuation: study treatment is permanently stopped earlier than the protocol-planned duration

An isolated bilirubin elevation is not typical for drug-induced liver injury. Bilirubin can be elevated either as part of a “Hy’s law” constellation with a preceding elevation of ALT/AST, or as part of a cholestatic reaction with simultaneous elevation of other cholestatic parameters (ALP, GGT). Isolated bilirubin elevation can be seen in conjunction with drugs that inhibit bilirubin conjugation or excretion, but both scenarios do not typically represent liver injury. Alternative causes of bilirubin elevation, including bilirubin interference (see [Section 8.4.1](#)) should be ruled out before basing dose modification decisions on bilirubin values alone

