PK blood sampling				Intensive PK in 12 Chinese adult participants and all Japanese pediatric participants (pre-dose, 2, 4, 6, 8, and 24 h post-dose) on day 14 after initial dose; Sparse PK in all participants: Pre-dose on day 15 after initial dose and pre-dose on day 15 after each new dose has started (dose reduction only)															
Hematological response assessment												X	X		X	X		X ²	
Survival follow-up			All participants will be followed for survival status every 3 months regardless of treatment discontinuation reason until study completion (Year 3), death, lost to follow-up, or withdrawal of consent for survival follow-up.														X		
Treatment compliance			S	S	S	S	S	S		S		S	S	S	S	S	X ² (S)	X ² (S)	
Disposition	X											X		X	X	X		At Year 3	
Prescription of eltrombopag		X	X	X	X	X	X	X	X		X	X	X	X					

Period	Screening	Core treatment part											Extension part		EOT		Long-term Follow-up	
		Day 1	Week 1	Week 2	Week 3 / 5 / 7	Week 4 / 8	Week 6	Week 9/11/15/17/19/21/23/25 when dose adjusted	Week 10/12/14/16/18/20/22/24	Week 13	Week 26	Week 28 to Week 50 ¹	Week 52	End of treatment	Safety follow-up	Survival follow-up	Year 2 / Year 3	
Visit Name	Screening																	
Days	-30 to -1	1	8	15	22 / 36 / 50	29 / 57	43	64 to 176	71 to 169	92	183	197 to 351	365	EOT	30 days after EOT	every 3 months	729 / 1093	
Prescription of r-ATG		Administered intravenously on Days 1 to 5																
Prescription of CsA		X	X	X	X	X	X	X	X	X	X	X	X	X	X ²	Monthly up to Year 2 ²		

^X Assessment to be recorded in the clinical database or received electronically from a vendor
^S Assessment to be recorded in the source documentation only
¹ Participants should visit hospital at least every 2 weeks until stabilization of dose; every 4 weeks after stabilization of dose.
² For participants that discontinue eltrombopag due to reasons other than non-response at W26, relapse or alternative SAA treatment
³ At Screening or Day 1
⁴ For participants who discontinue eltrombopag treatment prior week 26 or at visit week 26 a serum test is required at both visits. For participants who discontinue eltrombopag during extension part (week 28 to 50) or at visit week 52 a urine test is required at EOT only and serum test at the safety follow up visit.

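### Protocol Section 9.1.1, Table 6-7 and Table 8-1 disagree on whether CsA stops when eltrombopag is stopped for a Table 6-7 toxicity

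*Protocol*

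**What the plan says.** Protocol Section 6.1 fixes the term: "The study treatment includes eltrombopag, r-ATG and CsA".

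Section 9.1.1 opens its mandatory list with "Study treatment must be discontinued under the following circumstances". One entry is "Participant meets any of the stopping criteria in" Section 6.5.1. Table 6-7 belongs to Section 6.5.1.2, so its criteria fall under that entry.

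Table 6-7 uses two scopes:

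- **Eltrombopag only.** For isolated AST/ALT above 3 to 5 times ULN the row says "Discontinue participant from eltrombopag if elevation is combined with any of the following", and lists symptoms of liver injury or decompensation, and persistence of 4 weeks or more. For thrombosis or embolism it says "Discontinue participant from eltrombopag".
- **Study treatment.** The row for above 5 to 10 times ULN says "If not resolved within 28 days, then discontinue participant from study treatment". The rows for above 10 to 20 times ULN, above 20 times ULN, and combined transaminase and direct bilirubin elevation also name study treatment.

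The table's footnote then defines discontinuation, without distinguishing rows, as a permanent early stop of study treatment.

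In Table 8-1, the CsA prescription row runs past end of treatment to Year 2 under footnote 2: "For participants that discontinue eltrombopag due to reasons other than non-response at W26, relapse or alternative SAA treatment".

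**The concern.** A participant who meets a thrombosis or liver criterion has to be told which drugs to stop. The row in Table 6-7 names one drug, the mandatory list in Section 9.1.1 names a three-drug regimen, and the assessment schedule still has CsA being prescribed. Because r-ATG is given only on Days 1 to 5, the practical disagreement is almost entirely about CsA.

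At stake is, first, consistent management of participants who have had a toxicity stop. Second is what the later data represent. Sections 3, 8 and 9.1.1 keep early stoppers in efficacy assessment at Week 26 and beyond (until non-response at Week 26, relapse or alternative treatment), and Section 12.1 keeps them in the full analysis set. If sites read the passages differently, some of these participants will be assessed on CsA and some off it, by site interpretation and not by plan.

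**Working it through.** No arithmetic applies. The check is to follow each Table 6-7 discontinuation criterion through the four places that speak to it.

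| Criterion | Table 6-7 row | Table 6-7 footnote | Section 9.1.1 with Section 6.1 | Table 8-1 footnote 2, CsA row |
|---|---|---|---|---|
| Thrombosis/embolism | Eltrombopag stops; CsA not mentioned | Study treatment stops | All three drugs stop | CsA still prescribed to Year 2 |
| AST/ALT >3–5 × ULN, symptomatic or ≥4 weeks | Eltrombopag stops; CsA not mentioned | Study treatment stops | All three drugs stop | CsA still prescribed to Year 2 |
| AST/ALT >5–10 or >10–20 × ULN, unresolved in 28 days | Study treatment stops | Study treatment stops | All three drugs stop | CsA still prescribed to Year 2 |
| AST/ALT >20 × ULN | Study treatment stops | Study treatment stops | All three drugs stop | CsA still prescribed to Year 2 |
| Combined AST/ALT and direct bilirubin | Study treatment stops | Study treatment stops | All three drugs stop | CsA still prescribed to Year 2 |

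Three mismatches follow.

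1. In the first two lines the row names a narrower stop than both its own footnote and Section 9.1.1.
2. In every line footnote 2 leaves CsA prescribing open, since it excludes only non-response at Week 26, relapse and alternative SAA treatment. It therefore also disagrees with the rows that stop study treatment.
3. Nothing says which passage prevails. Section 6.5.1 calls permanent discontinuation mandatory for the events marked as such in Section 9.1.1. Section 6.1.5 says study treatment is discontinued in the extension part when a Section 9.1.1 criterion is met. Section 6.5.1.2 sends participants who meet the eltrombopag-discontinuation criteria on to Section 9.1. A site following the cross-references arrives at the conflict.

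Reporting was checked in the same way. Protocol Section 12.3 promises, for all three drugs, the number of participants with dose adjustments including permanent discontinuation, with reasons. In both SAPs (primary and final analysis), Section 2.4.1 has a subheading that names permanent discontinuations, but the text below it counts only reductions, increases and interruptions. Section 2.3.1 reports discontinuation by study phase, not by drug. Section 4 of each SAP does not list the omission as a change.

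There is one knock-on in the SAPs. Section 2.1.1 takes the last date of study treatment from any component. The concomitant-therapy summaries (Section 2.4.2) and laboratory summaries (Section 2.8.3) run to 30 days after it. Whether CsA continues therefore changes the length of those windows. The adverse-event on-treatment period is tied to eltrombopag and does not move.

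**The case against.** The best defence is that the passages can be read together.

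- **Table 6-7 is an eltrombopag guideline.** Its thrombosis and >3–5 × ULN rows are silent on CsA, which has its own rules in Sections 6.1.1.3 and 6.1.5. A site that stops eltrombopag under the table and the other drugs under Section 9.1.1 breaks neither. This stands in part: a reader might infer that Table 6-7 orders CsA to continue, and it does not. The row, its footnote and Section 9.1.1 still state different scopes, and the use of two terms in one table looks intended. The Amendment 3 summary says Section 6.5.1.2 was revised to make clear which term applies where.
- **Footnote 2 is a schedule note.** It also marks transfusion, response and compliance rows, and read literally it would continue CsA after pregnancy, which Sections 9.1.1 and 10.1.4 override. It is weak as a treatment order, but it is attached to the CsA prescription row and sites will use it there.
- **Section 9.1.1 may mean only the criteria worded as study treatment,** such as recurrent QTcF prolongation and the higher transaminase rows, and its link from Section 6.5.1.2 concerns action after discontinuation. That is arguable, but the entry says any criterion and carves out none.
- **Component-wise language exists.** Section 9.1.1 allows voluntary stopping of single drugs, its myelofibrosis footnote speaks of eltrombopag alone, and the SAP defines study treatment as any of the drugs. So it would be too strong to say that Section 9.1.1 never contemplates an eltrombopag-only stop. None of these limits the entry that points to Section 6.5.1.
- **Timing.** The last first visit was 03-Dec-2021, so two years of CsA ended around the turn of 2023 to 2024, before the final-analysis SAP of November 2024. Rewording after that cannot change management. That is correct, but it leaves the reporting gap untouched.

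**Conclusion.** The point holds as an internal inconsistency in current protocol text. After a thrombosis, or a symptomatic or persistent >3–5 × ULN elevation, the documents do not settle whether CsA stops. After the more severe liver criteria, Table 6-7 and Section 9.1.1 agree that study treatment stops, and only Table 8-1 differs. This rests on taking study treatment as Section 6.1 defines it.

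The size is unknown. The documents give no expected number of such stops and no evidence of how sites acted. The CR criteria, the denominator and the rule counting non-evaluable participants as non-responders are unaffected.

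Two stronger conclusions are tempting and unsupported. A reader might infer that each such participant puts 1/36 = 2.8 percentage points of the primary rate in doubt. That is only one participant's weight in a sample of 36; it becomes an effect only if CsA status changes the CR classification, which nothing here shows. A reader might also infer harm from the pivotal-study relapse data in Sections 1.1 and 4.2. Those data concern CsA maintenance after Month 6 in responders, so they say nothing about stopping CsA before Week 26. CsA use after Week 26 already varies by investigator discretion.

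**What to change.** Reconcile three places: Table 6-7 (rows and footnote), the Section 9.1.1 entry that points to Section 6.5.1, and Table 8-1 footnote 2 as applied to CsA prescription. Each stopping criterion should name which of eltrombopag, r-ATG and CsA is stopped, identically in all three. Which clinical rule applies is for the sponsor and investigators to settle.

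In the SAP, add permanent discontinuation and its reason, by drug, to the Section 2.4.1 dose-adjustment summary, so that it delivers what protocol Section 12.3 promises. No further split of Week 26 response by CsA status is recommended; it would probably cover too few participants to interpret.

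The wording change is short but needs a protocol amendment with its usual submissions, and it can affect management only while participants are still on treatment. The reporting change is one addition to an existing table, using dose records already collected on the dosage administration eCRF.
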